**Implementation Note:**

The vaccination arms receiving one dose will be shown at Days 1 and 8 only. Groups 1 and 3A will be shown at Days 1, 8, 29, and 36. Groups 3B and 4 will be shown at Days 1, 8, 85, and 92).

Tables with similar format:

**Table 320: Laboratory Summary Statistics by Parameter, Time Point, and Vaccination Arm – Aspartate Aminotransferase**

**Table 321: Laboratory Summary Statistics by Parameter, Time Point, and Vaccination Arm – Alkaline Phosphatase**

**Table 322: Laboratory Summary Statistics by Parameter, Time Point, and Vaccination Arm – Total Bilirubin**

**Table 323: Laboratory Summary Statistics by Parameter, Time Point, and Vaccination Arm – Creatine Kinase**

**Table 324: Laboratory Summary Statistics by Parameter, Time Point, and Vaccination Arm – Creatinine**

**14.3.5.2 Hematology Results****Table 325: Laboratory Results by Parameter, Maximum Severity, Time Point, and Vaccination Arm – Any Hematology Parameter**

Time Point	Vaccination Arm	N	None		Mild/ Grade 1 (Low)		Mild/ Grade 1 (High)		Moderate/ Grade 2 (Low)		Moderate/ Grade 2 (High)		Severe/ Grade 3 (Low)		Severe/ Grade 3 (High)		Missing	
			n	%	n	%	n	%	n	%	n	%	n	%	n	%	n	%
Baseline	Group 1: $5 \times 10^{10}$ vp ChAd/ 30 µg SAM-S	x	x	x	x	x	x	x	x	x	x	x	x	x	x	x	x	
	Group 3A: 30 µg SAM-S/ 30 µg SAM-S																	
	Group 3B: 30 µg SAM-S/ 3 µg SAM-S																	
	Group 4: 10 µg SAM-S-TCE/ 3 µg SAM-S-TCE																	
	Group 5: 3 µg SAM-S-TCE																	
	Group 6: 6 µg SAM-S-TCE																	
	Group 9: 3 µg SAM-S-TCE																	
	Group 10: 6 µg SAM-S-TCE																	
	Group 11: 10 µg SAM-S-TCE																	
	Group 13: $5 \times 10^{10}$ vp ChAd-S-TCE																	
	Group 14: $1 \times 10^{11}$ vp ChAd-S-TCE																	
	Group 15: $5 \times 10^{11}$ vp ChAd-S-TCE																	
All Participants																		

Time Point	Vaccination Arm	N	None		Mild/ Grade 1 (Low)		Mild/ Grade 1 (High)		Moderate/ Grade 2 (Low)		Moderate/ Grade 2 (High)		Severe/ Grade 3 (Low)		Severe/ Grade 3 (High)		Missing	
			n	%	n	%	n	%	n	%	n	%	n	%	n	%	n	%
Day 8	...																	
Day 29 (pre-dose 2 for Groups 1 and 3A)	...																	
Day 36 (8 days post-dose 2 for Groups 3A and 4)	...																	
Day 85 (pre-dose 2 for Groups 3B and 4)	...																	
Day 92 (8 days post-dose 2 for Groups 3B and 4)	...																	
Max Severity Post Baseline	...																	

Note: The “Maximum Post Baseline” rows indicate the maximum severity experienced by each vaccination group at any time point post baseline, including unscheduled assessments.  
N = Number of participants in the Safety Analysis Population

## Implementation Note:

The vaccination arms receiving one dose will be shown at Days 1 and 8 only. Groups 1 and 3A will be shown at Days 1, 8, 29, and 36. Groups 3B and 4 will be shown at Days 1, 8, 85, and 92). All vaccination arms will be shown in the Max Severity Post-Baseline row.

Tables with similar format:

**Table 326: Laboratory Results by Parameter, Maximum Severity, Time Point, and Vaccination Arm – White Blood Cells**

**Table 327: Laboratory Results by Parameter, Maximum Severity, Time Point, and Vaccination Arm – Hemoglobin**

**Table 328: Laboratory Results by Parameter, Maximum Severity, Time Point, and Vaccination Arm – Platelets**

**Table 329: Laboratory Summary Statistics by Parameter, Time Point, and Vaccination Arm – White Blood Cells**

Time Point	Vaccination Arm	N	Mean	Standard Deviation	Median	Min, Max
Baseline	Group 1: $5 \times 10^{10}$ vp ChAd/ 30 $\mu$ g SAM-S	x	xx.x	xx.x	xx.x	xx.x, xx.x
	Group 3A: 30 $\mu$ g SAM-S/ 30 $\mu$ g SAM-S					
	Group 3B: 30 $\mu$ g SAM-S/ 3 $\mu$ g SAM-S					
	Group 4: 10 $\mu$ g SAM-S-TCE/ 3 $\mu$ g SAM-S-TCE					
	Group 5: 3 $\mu$ g SAM-S-TCE					
	Group 6: 6 $\mu$ g SAM-S-TCE					
	Group 9: 3 $\mu$ g SAM-S-TCE					
	Group 10: 6 $\mu$ g SAM-S-TCE					
	Group 11: 10 $\mu$ g SAM-S-TCE					
	Group 13: $5 \times 10^{10}$ vp ChAd-S-TCE					
	Group 14: $1 \times 10^{11}$ vp ChAd-S-TCE					
	Group 15: $5 \times 10^{11}$ vp ChAd-S-TCE					
All Participants						
Day 8	...					
Day 8, Change from Baseline	...					
Day 29 (pre-dose 2 for Groups 1 and 3A)	...					
Day 29, Change from Baseline						
Day 36 (8 days post-dose 2 for Groups 3A and 4)						
Day 36, Change from Baseline						
Day 85 (pre-dose 2 for Groups 3B and 4)						
Day 85, Change from Baseline						
Day 92 (8 days post-dose 2 for Groups 3B and 4)						
Day 92, Change from Baseline						

Note: N = Number of participants in safety population

**Implementation Note:**

The vaccination arms receiving one dose will be shown at Days 1 and 8 only. Groups 1 and 3A will be shown at Days 1, 8, 29, and 36. Groups 3B and 4 will be shown at Days 1, 8, 85, and 92).

Tables with similar format:

**Table 330: Laboratory Summary Statistics by Parameter, Time Point, and Vaccination Arm – Hemoglobin**

**Table 331: Laboratory Summary Statistics by Parameter, Time Point, and Vaccination Arm – Platelets**

### 14.3.6 Displays of Vital Signs

**Table 332: Vital Signs by Assessment, Maximum Severity, Time Point, and Vaccination Arm – Any Assessment**

Time Point	Vaccination Arm	N	None		Mild		Moderate		Severe		Missing	
			n	%	n	%	n	%	n	%	n	%
Baseline	Group 1: $5 \times 10^{10}$ vp ChAd/ 30 µg SAM-S	x	x	xx	x	xx	x	xx	x	xx	x	xx
	Group 3A: 30 µg SAM-S/ 30 µg SAM-S											
	Group 3B: 30 µg SAM-S/ 3 µg SAM-S											
	Group 4: 10 µg SAM-S-TCE/ 3 µg SAM-S-TCE											
	Group 5: 3 µg SAM-S-TCE											
	Group 6: 6 µg SAM-S-TCE											
	Group 9: 3 µg SAM-S-TCE											
	Group 10: 6 µg SAM-S-TCE											
	Group 11: 10 µg SAM-S-TCE											
	Group 13: $5 \times 10^{10}$ vp ChAd-S-TCE											
	Group 14: $1 \times 10^{11}$ vp ChAd-S-TCE											
	Group 15: $5 \times 10^{11}$ vp ChAd-S-TCE											
	All Participants											
Day 2												
Day 8	...											
Day 15												
Day 29	...											
Day 36	...											
Day 43	...											
Day 57	...											
Day 85												

Time Point	Vaccination Arm	N	None		Mild		Moderate		Severe		Missing	
			n	%	n	%	n	%	n	%	n	%
Day 86												
Day 92												
Day 99												
Day 113												
Day 169												
Day 181												
Day 209												
Day 265												
Day 366												
Day 394	...											
Day 450												
Max Severity Post Baseline	...											

Note: The “Max Post Baseline” rows indicate the maximum severity experienced by each participant at any time point post baseline, including unscheduled assessments.  
N = Number of participants in the safety population.

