### 3.1. Study Definitions and Derived Variables

Vital signs, including oral temperature, pulse, and blood pressure (BP), and clinical laboratory parameters obtained prior to the first study vaccination will be considered as baseline. Blood drawn for cellular immunology assays, antibody assays, and transcriptomal assays (groups 5-11, 13-15 only) prior to the first dose of study product will be considered as baseline in immunogenicity analyses.

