#### Adverse Events

AE means any untoward medical occurrence associated with the use of an intervention in humans, whether or not considered intervention-related [21 CFR 312.32 (a)]. An AE can therefore be any unfavorable and unintended sign, symptom or disease temporally associated with the use of medicinal (investigational) product.

Any medical condition that is present at the time that the participant is screened will be considered as baseline and not reported as an AE. However, if the severity of any pre-existing medical condition increases, it will be recorded as an AE.

AEs can be further divided into solicited AEs and unsolicited AEs. Solicited AEs are those that are described in the package insert as local or systemic reactogenicity occurring in the first 7 days after vaccination. Unsolicited AEs are those events that the participant reports occurring without being queried about the specific event.

AEs will be assessed for severity and relationship to study intervention. Reporting of all AEs, solicited and unsolicited, will occur during the period from study product administration on Day 1 through 28 days after each vaccination. After 28 days post last vaccination through the end of study, only SAEs, protocol specified AESIs (including PIMMCs, MAAEs, and NOCMCs), and AEs leading to withdrawal from the study will be reported.

All AEs, solicited and unsolicited, will be captured on the appropriate DCF. Solicited AEs will be regarded as related to the study product and will not require separate entry into the AE log. Information to be collected for unsolicited AEs includes event description, date of onset, assessment of severity, relationship to study product and alternate etiology (assessed only by those with the training and authority to make a diagnosis and listed on the Form FDA 1572 as the participating site PI or appropriate sub-investigator), date of resolution, seriousness, and outcome. AEs occurring during the study-collection and reporting period will be documented appropriately regardless of relationship.

AEs will be followed to resolution or stabilization.

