## 9.6. Clinical Laboratory Evaluations

Chemistry parameters measured include alanine aminotransferase, aspartate aminotransferase, alkaline phosphatase, total bilirubin, creatine kinase, and creatinine. Hematology parameters measure include white blood cells, hemoglobin, and platelets.

Summaries of clinical laboratory data are grouped by vaccination arm, severity for each visit, and the maximum over all post-vaccination visits. Summaries are shown for each chemistry parameter and all chemistry parameters combined ([Table 312](#), [Table 313](#), [Table 314](#), [Table 315](#), [Table 316](#), [Table 317](#), and [Table 318](#)) and for each hematology parameter and all hematology parameters combined ([Table 325](#), [Table 326](#), [Table 327](#), and [Table 328](#)). Clinical laboratory results and change from baseline are also summarized by mean, standard deviation, median, minimum, and maximum for each chemistry parameter ([Table 319](#), [Table 320](#), [Table 321](#), [Table 322](#), [Table 323](#), and [Table 324](#)) and for each hematology parameter ([Table 329](#), [Table 330](#), and [Table 331](#)). Bar graphs of clinical laboratory results by maximum severity post baseline and vaccination arm will be presented [Figure 664](#), [Figure 665](#), [Figure 666](#), [Figure 667](#), and [Figure 668](#)).

Individual participant listings for abnormal chemistry results ([Table 310](#)) and abnormal hematology results ([Table 311](#)) will be presented.

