## 9.1 Overall Study Design and Plan Description

See [Table 2](#).

**9.5.1 Efficacy/Immunogenicity and Safety Measurements Assessed and Flow Chart****Table 6: Schedule of Activities - COVID-19 Vaccination Naïve, 18-60 years of age, Groups 1 and 3A**

Study Visit	V00	V01	V02	V03	V04	V05	V06	V07	V08	V08A	V09	V10	V11	Unsc	Early Term
Study Day post 1 st Study Vaccination	Scr-30d to -1d	D1	D2+1d	D4+2d	D8 +2d	D29±3d	D30+1d	D32+2d	D36+2d	D43+4wk	D57±3d	D209±14d	D394±14d		
Study Day post 2 nd Study Vaccination						D1	D2+1d	D4+2d	D8+2d	D15+4wk	D29±3d	D181±14d	D366±14d		
Obtain Written Informed Consent	X									X					
Review Eligibility Criteria	X	X				X				X					
Medical History	X														
Review Interim Medical History		X	X	X	X	X	X	X	X	X	X	X	X	X	X
Concomitant Medications	X	X	X	X	X	X	X	X	X	X	X	X	X	X	X
Vital Signs (Oral Temp, Pulse, BP)	X	X			X	X			X	X	X	X	X	X	X
Physical Examination including Height and Weight	X														
Targeted PE, if indicated		X			X	X			X	X	X	X	X	X	X
Serum or Urine Pregnancy Test	X	X				X				X					
Nasal Swab Collection for SARS-CoV-2 PCR	X					X									
Blood Collection for Safety Labs	X 				X 	X 			X 	X 				X 	X 
Blood Collection for HBsAg, Anti-HCV, SARS-CoV-2 serology, HIV	X					X 									
Blood Collection for ELISpot		X				X					X	X	X	X	X
Blood Collection for ICS Assays		X				X					X			X	X
Blood Collection for Antibody Assays		X				X					X	X	X	X	X
Blood Collection for PBMC and Plasma Storage		X			X	X			X		X	X	X	X	X

Study Visit	V00	V01	V02	V03	V04	V05	V06	V07	V08	V08A	V09	V10	V11	Unsc	Early Term
Study Day post 1 st Study Vaccination	Scr-30d to -1d	D1	D2+1d	D4+2d	D8 +2d	D29±3d	D30+1d	D32+2d	D36+2d	D43+4wk	D57±3d	D209±14d	D394±14d		
Study Day post 2 nd Study Vaccination						D1	D2+1d	D4+2d	D8+2d	D15+4wk	D29±3d	D181±14d	D366±14d		
Enroll in Advantage eClinical		X													
Study Vaccination		X				X									
45 Minute Evaluation After Study Vaccination		X				X									
Distribute Memory Aid and Study Related Materials		X				X									
Review Memory Aid			X	X	X		X	X	X					X 	X 
Adverse Events		X	X	X	X	X	X	X	X		X			X 	X 
SAEs/AESIs including PIMMCs/MAAEs/NOCMCs		X	X	X	X	X	X	X	X	X 	X	X	X	X	X
Optional Leukapheresis 										X					
Saliva Collection for Antibodies			X			X				X					

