## Implementation Note:

The vaccination arms receiving one dose will be shown at Days 1 and 8 only. Groups 1 and 3A will be shown at Days 1, 8, 29, and 36. Groups 3B and 4 will be shown at Days 1, 8, 85, and 92). All vaccination arms will be shown in the Max Severity Post-Baseline row.

Tables with similar format:

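### The maximum post-baseline severity rows for laboratory values and vital signs ignore each participant's own baseline grade, so persisting abnormalities are tabulated together with new ones

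*SAP*

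**What the plan says.** The note to Table 332 (Section 14.3.6, vital signs) says that the maximum "rows indicate the maximum severity experienced by each participant at any time point post baseline, including unscheduled assessments". The chemistry note under Table 312 uses the same rule. The hematology note under Table 325 says "rows indicate the maximum severity experienced by each vaccination group at any time point post baseline, including unscheduled assessments", with group in place of participant. That looks like a wording slip, since the table counts participants. The rule covers Tables 312-318, 325-328 and 332-336. Section 9.6 describes the laboratory summaries as grouped by arm, "severity for each visit, and the maximum over all post-vaccination visits".

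Section 3.1 fixes baseline: "clinical laboratory parameters obtained prior to the first study vaccination will be considered as baseline", and likewise for vital signs. Samples taken before dose 2 are therefore post-baseline.

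Figures 664-668 plot the maximum post-baseline laboratory grade, and their implementation note leaves out screening laboratory results. Laboratory values also have change from baseline as mean, SD, median, minimum and maximum (Tables 319-324 and 329-331). Section 9.7 plans no change or shift summary for vital signs. Section 4.2 states that there is no control group, and Section 6.8 that there is no formal testing.

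**The concern.** A participant with a Grade 1 systolic pressure before dosing and the same grade at a later visit enters the maximum row as a post-baseline Grade 1, exactly like someone whose pressure rose after vaccination.

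Safety is the primary objective, and Section 4.5 names laboratory results among the sources of the safety endpoints. Without a control group, each participant's own baseline is the main comparator available, and the maximum row does not use it. With 3 to 12 participants per arm (Table 2), one persisting abnormality moves a row by 1/12 = 8 to 1/3 = 33 percentage points.

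**Working it through.** The SAP gives no figure on this point, so the check is of definitions first and size second.

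**1. Can the Baseline row repair the maximum row?** Take an arm of n participants with b abnormal at baseline and m in the maximum row. The number newly abnormal lies anywhere between max(0, m − b) and min(m, n − b). As an illustration, n = 8 and b = m = 2 gives 0 to 2: the same two people, or two different people. Group distributions cannot settle which.

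**2. Can the other summaries repair it?** Mean change from baseline for laboratory values does not show who moved up a grade. Vital signs have no such table. In Tables 6-8 the pre-first-dose safety laboratory sample is at screening and none is marked on Day 1. Because Figures 664-668 exclude screening results, by those schedules they show no baseline at all.

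**3. How many visits feed the maximum?** Counted from the row "Vital Signs (Oral Temp, Pulse, BP") in Tables 6-8, without screening, Day 1, unscheduled, early-termination and optional leukapheresis visits:

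- Groups 1 and 3A: Days 8, 29, 36, 57, 209, 394 = 6
- Stage 2 groups: Days 2, 8, 15, 29, 85, 181, 366 = 7
- Groups 3B and 4: Days 8, 29, 57, 85, 86, 92, 99, 113, 169, 265, 450 = 11

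The optional leukapheresis visit makes these 7, 8 and 12. Scheduled laboratory visits are far fewer: "The vaccination arms receiving one dose will be shown at Days 1 and 8 only", which is 1 post-baseline visit, against 3 in the two-dose arms.

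**4. Size with no vaccine effect.** The SAP gives no background rates, so the per-visit chance p of any graded value and the within-person correlation ρ are assumptions. With independent visits, the chance of entering the row is 1 − (1 − p)^k. (The same formula reproduces SAP Table 4: 7 participants at 10% give 52.2%.) With correlation, a beta-binomial model with a = p(1 − ρ)/ρ and b = (1 − p)(1 − ρ)/ρ gives S_k = Π(b + i)/(a + b + i) for i = 0 to k − 1. The chance is then 1 − S_k, and the share of those in the row who were already abnormal at baseline is [p − (S_k − S_{k+1})]/(1 − S_k). At p = 5%:

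| ρ | In row: 6 visits | 7 visits | 11 visits | Already abnormal at baseline (6 / 7 / 11) |
|---|---|---|---|---|
| 0 | 26.5% | 30.2% | 43.1% | 5 / 5 / 5% |
| 0.3 | 15.7% | 16.9% | 20.5% | 24 / 23 / 21% |
| 0.6 | 10.1% | 10.5% | 11.8% | 45 / 44 / 40% |

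With independent visits, p = 2% gives 11.4, 13.2 and 19.9%, and p = 10% gives 46.9, 52.2 and 68.6%.

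For laboratory values in a one-dose arm, the chance that a participant with a graded Day 8 value was also graded at baseline is p + ρ(1 − p). At p = 5% and ρ = 0.6 that is 0.05 + 0.6 × 0.95 = 62%.

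The two effects trade off. If abnormalities persist, many people in the row were abnormal before dosing and visit count matters little. If they fluctuate independently, the reverse holds.

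**The case against.** The row is labelled and defined accurately, the analysis is descriptive, and the same tables carry a Baseline row and a row per visit. Listings 12-14 give every value by participant and time point, with the grade for abnormal results, so with at most 12 people per arm a determined reader can make the comparison by hand. This stands, and it makes the point a weakness of the summary displays rather than a wrong inference. Eligibility limits in the protocol, which is not at hand, may also lower the rate of baseline abnormality.

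Several stronger readings are tempting, and the SAP does not support them.

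- *The rows contradict Section 4.5.* That section says "Any medical condition that is present at the time that the participant is screened will be considered as baseline and not reported" as an AE, and that "if the severity of any pre-existing medical condition increases, it will be recorded as an AE". It governs what is recorded as an adverse event. The tables at issue summarise graded measurements. Adverse events of these kinds have their own rows in Table 212, although the SAP does not say how those rows are derived.
- *Arms differ through visit count alone.* Counts are equal within each of the three schedules, so dose comparisons within a schedule are untouched. Six against seven visits is minor. The large contrast is Groups 3B and 4, with 7 + 3 = 10 participants, against the rest.
- *The row mainly reflects background.* This cannot be shown. It depends on assumed rates and correlation, and the independent-visit percentages do not fit an explanation by chronic blood pressure, which persists within a person.
- *The vital-sign maximum should stop 28 days after each dose.* That would still leave 4, 4 and 6 scheduled visits (34, 34 and 47% at p = 10% with independent visits) and would drop late readings from a trial with 12-month follow-up.

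**Conclusion.** The point holds for the missing baseline comparison. As defined, the maximum rows and Figures 664-668 combine new, worsened and persisting abnormalities, and no planned summary table separates them. This applies to every arm and to both laboratory values and vital signs.

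Its size is not known from the SAP. At an assumed 5% per-visit rate, the part of the vital-sign maximum row that was already abnormal at baseline runs from 5% (independent visits) to 40-45% (correlation 0.6). The baseline reading itself is never counted; an earlier abnormality enters only if it is seen again after dosing.

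The visit-count effect is secondary. It concerns vital signs compared across schedules and calls for a footnote. No planned test is affected. This is an inexpensive improvement to the safety reporting.

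**What to change.** - Keep the existing maximum row.
- In Tables 312-318, 325-328 and 332-336, add a row counting participants whose maximum post-baseline grade exceeds their own baseline grade, and produce a matching version of Figures 664-668.
- Add baseline-by-maximum grade shift counts for laboratory values and vital signs. Use the Section 3.1 baseline, compare low and high grades in their own direction, and build the any-parameter tables from parameter-level comparisons, so that one abnormal parameter at baseline does not hide a new abnormality in another.
- Footnote the vital-sign tables: scheduled post-baseline visits number 6 (Groups 1 and 3A), 7 (Stage 2) and 11 (Groups 3B and 4), so maximum rows should not be compared across schedules. Comparisons within a schedule are unaffected.
- Align the Table 325 note with the per-participant wording of the other two.

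The cost is one derived variable, some extra table rows and one more version of five figures. All the data are already collected, and nothing now planned is removed.

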## Implementation Note:

The vaccination arms shown at each time point will vary. Vaccination arms will be shown at each time point where vital signs were assessed.

Tables with similar format:

**Table 333: Vital Signs by Assessment, Maximum Severity, Time Point, and Vaccination Arm – Temperature**

**Table 334: Vital Signs by Assessment, Maximum Severity, Time Point, and Vaccination Arm – Diastolic Blood Pressure**

**Table 335: Vital Signs by Assessment, Maximum Severity, Time Point, and Vaccination Arm – Systolic Blood Pressure**

**Table 336: Vital Signs by Assessment, Maximum Severity, Time Point, and Vaccination Arm – Pulse**

#### 14.4 Summary of Concomitant Medications

**Table 337: Number and Percentage of Participants with Prior and Concurrent Medications by WHODrug Classification and Vaccination Arm – COVID-19 Vaccination Naïve, 18-60 years of age, Groups 1 and 3A**

WHODrug Code Level 1, Anatomic Group	WHODrug Code Level 2, Therapeutic Subgroup	Group 1: $5 \times 10^{10}$ vp ChAd/ 30 µg SAM-S (N=X)		Group 3A: 30 µg SAM-S/ 30 µg SAM-S (N=X)		All Participants (N=X)	
		n	%	n	%	n	%
Any Level 1 Codes	Any Level 2 Codes	x	xx	x	xx	x	xx
[ATC Level 1 - 1]	Any [ATC 1 – 1]						
	[ATC 2 - 1]						
	[ATC 2 - 2]						
	[ATC 2 - 3]						
[ATC Level 1 – 2]	[ATC 2 - 1]						
	[ATC 2 - 2]						
	[ATC 2 - 3]						

Tables with similar format:

**Table 338: Number and Percentage of Participants with Prior and Concurrent Medications by WHODrug Classification and Vaccination Arm – COVID-19 Vaccination Naïve, 18-60 years of age, Groups 3B and 4**

**Table 339: Number and Percentage of Participants with Prior and Concurrent Medications by WHODrug Classification and Vaccination Arm – COVID-19 mRNA Vaccinated, 18-60 years of age, SAM-S-TCE Boosts**

**Table 340: Number and Percentage of Participants with Prior and Concurrent Medications by WHODrug Classification and Vaccination Arm – COVID-19 mRNA Vaccinated, >60 years of age, SAM-S-TCE Boosts**

**Table 341: Number and Percentage of Participants with Prior and Concurrent Medications by WHODrug Classification and Vaccination Arm – COVID-19 mRNA Vaccinated, >60 years of age, ChAd-S-TCE Boosts**

